2.5 Aspirin as a potential treatment

Two randomised trials of oral aspirin in addition to compression have been reported.^{30,31} Combined into a meta-analysis (figure 1), the pooled healing rate favoured 300 mg aspirin at 16 weeks (RR 1.62, 95%CI 0.99 – 2.65). However, there are methodological issues with these trials. Both trials excluded patients commonly seen in clinical care who would be treated with compression – those with small ulcers or those with slightly reduced blood flow to the lower leg (ankle brachial index 0.8 to 0.9). Further, the trial regimens likely excluded many of the very old (who have increased incidence of VLU) as the average ages in the trials were 64.1 years and 59.5 years. Most importantly, the trials were too small to provide the substantive evidence needed to change current practice.

[figure not shown]

Figure 1. Meta-analysis of two trials of comparing aspirin plus compression to placebo plus compression

Platelet inhibition by aspirin is achieved by doses lower than 300 mg. However, variability in response to low-dose aspirin, independent of compliance, has been described. Aspirin formulation, obesity, and rate of platelet turnover are all associated with low response.³² While a 150 mg dose is at the higher end of the low-dose range,³³ it offers a responsible compromise dose that allows for variability in response to low-dose aspirin as well as increased risk with the very old. A secondary analysis of data from the HALT trial (led by the applicant, n=368)⁸ found 150mg aspirin was associated with the strongest effect on VLU healing rates, (adjusted for baseline ulcer size and duration, Hazard Ratio 1.77, 95%CI 1.13–2.75).

Anecdotally, the main barrier to further testing of aspirin for VLU healing has been the view that it would be difficult to recruit VLU patients, as many would be older adults thought to already be taking aspirin for other indications. However, two New Zealand VLU trials showed aspirin use was only 30% of participants in one (recruitment 2003-2005) and 17% in the second (recruitment 2007).⁸ The low use of aspirin was not explained by contraindications. These findings are similar to the 34% of VLU patients taking aspirin in a 2010 audit of 50 VLU patients in Christchurch (pers.comm., [name]).

2.6 Biological plausibility of aspirin as treatment for venous ulcers

Venous ulceration is the most severe presentation of chronic venous insufficiency (CVI). It results from a chronic inflammatory process that starts with the haemodynamic forces (turbulent blood flow and altered shear stress) produced by venous hypertension, activating leukocytes and causing platelet aggregation (Figure 2). The activated leukocytes initiate an acute inflammatory response in CVI that becomes a chronic inflammatory state as inflammatory mediators remain upregulated.^{35,36} Patients with CVI have significantly higher platelet counts compared to normal controls or people with other endogenous inflammatory disease or non-venous leg ulcers.^{37,38} Accompanying leukocyte activation, the aggregated platelets also become activated. Platelets in patients with CVI have also

[figure not shown]

Figure 2: Simplified outline of pathophysiology of venous ulceration.

been found to have increased reactivity compared to normal controls,³⁹ and the number of platelet microparticles (shed by activated platelets) are significantly increased in people with CVI compared to normal controls.³⁸ Activated platelets appear also to be involved in the chronic inflammatory processes through production of CD40 ligands that prompt endothelial cells to produce inflammatory process components including reactive oxygen species, chemokines, and adhesion molecules.^{40,41} Activated platelets also influence cellular adhesion directly (P-selectin expression) and indirectly (through synthesis of interleukin-1 β), release extracellular matrix-degrading matrix metalloproteases (MMP-2 and MMP-9) and chemokines that trigger recruitment of monocytes or promote differentiation of monocytes into macrophages to maintain inflammation.

Aspirin could plausibly affect venous ulcer healing through two actions. First, aspirin inhibits platelet aggregation (and hence activation) through the irreversible inhibition of platelet cyclooxygenase. Aspirin also inhibits vessel-wall cyclooxygenase through the blocking prostacyclin synthesis, although it requires higher doses of aspirin to achieve vessel-wall inhibition of cyclooxygenase than platelet cyclooxygenase;⁴² synthesis in venous-wall tissue is inhibited by doses of aspirin greater than 81mg.⁴³ Second, aspirin, through inhibiting the cyclooxygenase pathway, may also have an effect on inflammation.⁴⁴ Prostaglandins are released during the inflammatory response and may amplify blood vessel permeability through the mediators such as histamine and bradykinin.⁴⁵ The need for cheap, easily accessible adjuvant treatments, the emerging role of platelets in the pathophysiology

of venous ulceration and the positive randomised pilot evidence all suggest the need for a definitive randomised controlled trial of aspirin as an adjuvant treatment for venous ulceration.

2.7 Clinical Safety Summary

Low dose enteric coated aspirin is licensed for general sale in New Zealand and can be purchased over the counter without a prescription. It is considered a relatively safe medication. The main side effects of aspirin are gastrointestinal upset and bleeding, but the absolute risk of major gastrointestinal bleeding in primary prevention is small. The Antithrombotic Trialists Collaboration found the rate of extra-cranial bleeds (which were mainly composed of gastrointestinal bleeds) in five primary prevention trials of daily aspirin (n=96,456, mean follow up 7 years) was only slightly increased compared to controls treated with placebo (0.10% in aspirin-treated patients compared to 0.07% in patients who did not receive aspirin, an annual absolute increase of three events per 10,000 patients receiving aspirin).⁴⁶ There was also a small increase in the rate of haemorrhagic strokes (0.04% in aspirin-treated patients compared to 0.03% in controls, an annual absolute increase of one event per 10,000 patients receiving aspirin). This increase in haemorrhagic stroke was offset by a small decrease in the rate of ischaemic stroke (0.16% in aspirin-treated patients compared with 0.18% in controls, an annual absolute decrease of two events per 10,000 patients receiving aspirin). The doses used in the studies ranged from 75 mg daily to 500 mg daily but the effect of dose on bleeds was not examined. However, a large population-based study of 2,105 cases with upper gastrointestinal bleeding or perforation obtained from the UK-based General Practice Register and 11,500 randomly sampled controls found 150 mg daily doses were associated with an equal risk of bleeding (RR 2.0, 95%CI 1.5 to 2.6) to that of 300 mg doses (RR 2.0, 95%CI 1.4 to 2.8), and only slightly more than that seen with 75 mg daily doses (RR 1.9, 95%CI 1.6 to 2.4).⁴⁷

The risk of bleeding is increased with age, diabetes and smoking. The US Preventive Services Task Force states the evidence is insufficient to determine a risk/benefit for cardiovascular disease prevention in people aged over 80 years.⁴⁸ Approximately one third of participants in our large New Zealand VLU (HALT) trial were aged 80 or older.⁸ However, equipoise does exist and a large Australian primary prevention trial is now underway with 100mg aspirin in participants aged 70 years or older.⁴⁹ Excluding patients older than 79 years would reduce the generalisability of any VLU trial when more evidence is needed in order to determine risk/benefit for the older age group.

2.8 Rationale for a clinical trial

The ageing population and substantial anticipated increase in people with VLU (especially in the very old), the need for cheap, accessible adjuvant treatments, the role of platelets in the pathophysiology of VLU and the encouraging evidence for aspirin all point to the need for a definitive randomised controlled trial of low dose aspirin as an adjuvant treatment for VLU using a trial population that is as open as clinically possible and thus similar to that encountered every day in clinical practice.

[figure not shown]
3. Objectives

The main aim of this trial is to evaluate the effectiveness of low dose aspirin compared to placebo when used in addition to compression therapy for VLU time-to-healing over 24 weeks follow up. Other aims include estimating the effect of aspirin on proportion of patients healed, adverse events, adherence and health-related quality of life (HRQoL).

4. Trial Design

A prospective community-based, double-blind, placebo-controlled, randomised trial with participants receiving either 150 mg aspirin daily for up to 24 weeks or matching placebo. Block randomisation will be used, stratified by trial centre and prognostic index (ulcer size and duration) to ensure a balance of participants within trial centres and for participants likely to be slow healers. Participants in both arms will also receive compression therapy (with system of choice guided by patient and/or clinical preference) as delivered through district nursing services at the trial centres. The district nurse will identify potential participants, obtain verbal consent from them to be contacted by the research nurse if the patient is interested in the trial and notify the research nurse at each trial centre.

5. Trial Plan Schematic

6. Recruitment

6.1 Recruitment source & process

Patients with venous leg ulcers who present for treatment to or already receiving treatment from the community-based district nursing services at trial centres previously involved in the National Institute of Health Innovation's (NIHI) leg ulcer trials will be recruited. These centres are based within Auckland, Counties Manukau, Waikato, and Southern District Health Boards, and Nurse Maude community nursing services in Christchurch. The same model of recruitment is used as was successfully employed in previous venous leg ulcer trials in New Zealand (figure 4). A 0.5 FTE Research Nurse will be seconded to the trial from each trial centre (employing authority will be reimbursed).

The District Nurse will identify potential participants, obtain verbal consent from them to be contacted by the Research Nurse if the patient is interested in the trial and notify the research nurse at each trial centre. The Research Nurse will screen the patients for eligibility. Eligible patients will be consented, assessed, and randomised by the Research Nurse at a location convenient to the patient. The location may be a clinic, the patient's home or workplace. Once randomised, the participant will receive the allocated treatment from the Research Nurse, who will also conduct the endpoint visits at 24 weeks after randomisation, again at a location convenient to the participant. In between Research Nurse visits the participants will continue to receive normal care by the District Nurses.

[figure not shown]

Figure 3: Flow chart of proposed study.

6.2 Case definition

Only patients with venous leg ulcers being treated through the trial centres will be recruited. A patient will be considered to have a purely venous leg ulcer where other causative aetiologies (diabetes, rheumatoid arthritis, malignancy) have been ruled out, the ulcer appears clinically venous (presentation may include any or all of the following: moist, shallow, irregular shape; haemosiderian pigmentation; venous eczema; ankle oedema; ankle flare; lipodermatosclerosis), and the trial participant has an Ankle Brachial Index (ABI) ≥ 0.8 to rule out arterial insufficiency. For the purposes of this trial, an incident leg ulcer will be considered to be any break in the skin on the leg (below the knee) that has been present for four or more weeks. If a patient known to a service presents with a new episode of ulceration, has a prior history of venous leg ulceration, is considered to have a

current venous leg ulcer, they will be candidates for participation. Patients with prevalent ulcers meeting the case definition already in treatment will also be eligible for inclusion.

6.3 Eligibility criteria

Patients with leg ulcers will be eligible for *inclusion* if they meet the following criteria:

- Aged 18 years or older
- Determined to have a venous leg ulcer (clinical indications of venous ulceration, ABI \geq 0.8, and other causative aetiologies ruled out)
- Able to tolerate compression therapy
- Able to provide written informed consent
- Confirmation with participant's general practitioner that the participant can take low dose aspirin or placebo.

Potentially eligible participants will be *excluded* if they meet any of the criteria below:

- Pregnant or breast-feeding women
- History of myocardial infarction, stroke, transient ischaemic attack, angina or significant peripheral arterial disease
- History of adverse effects related to aspirin use
- Currently using aspirin, or other anti-platelet or anticoagulant therapy
- Participant has any other existing condition or treatment that is a contraindication to use of aspirin or to participation in the trial
- Participant has any other existing condition where treatment with aspirin is indicated.

7. Randomisation and allocation concealment

On registration (week -1) participants will be assigned a unique sequential registration number using numbers generated by the NIHI data management. When a registration number has been allocated, the participant's initials and date of birth and the date of registration must be recorded. This registration number will be used to identify the participant throughout all periods of the trial. Once a registration number has been assigned, it may not be used again.

Immediately after baseline data have been recorded, consented patients who fulfil entry criteria will be randomised by computer to one of the two trial groups using stratified blocked randomisation with varying block sizes of 2 and 4. The randomisation sequence will be prepared by the trial statistician and loaded into a secure database. Randomisation will be stratified by trial centre and prognostic index (based on ulcer and duration) which will isolate any centre effect in clinical management and ensure a balance on key prognostic variables known to influence healing at 24 weeks. Each treatment pack is uniquely numbered and is allocated using the randomisation sequence. The Research Nurse accesses the randomisation web-page, completes data entry, and generates the allocation using a computerised tablet. The allocated treatment is then given to the participant by the Research Nurse.

8. Concomitant Therapy

If a concurrent medication or therapy is administered, the generic name of the medication or supplement and the date(s) and frequency of administration will be recorded on “Concomitant Medication” Case Report Form (CRF) M. Throughout the trial, the participant’s general practitioner, nurse practitioner or consultant specialists are free to provide whatever ancillary treatments are required for the appropriate medical management of trial subjects. Where treatment is necessary by procedure or medication for which aspirin is contraindicated, participants should stop taking the trial treatment.

9. Withdrawal criteria

If, at any time after randomisation, significant intolerance to the trial treatment is suspected, the trial treatment can be discontinued. Should participants require discontinuation of trial treatment for any reason (see below), or if they elect to cease taking treatment, follow-up visits and data collection will continue as scheduled as if they were continuing with the randomised treatment. Participants may have the trial treatment discontinued if one or more of the following occurs:

- The participant makes a voluntary decision to withdraw from follow-up, or from the treatment.
- The participant has a serious clinical adverse event, intercurrent illness, or other medical condition that indicates to the clinical team that continued treatment with the trial medication is not in the best interest of the participant. The trial treatment will be discontinued if the participant develops any life threatening or seriously disabling illness or is admitted to hospital.
- The trial is terminated.

If the participant discontinues treatment due to a serious adverse event, the participant will be followed until the event resolves or there is a return to a clinically acceptable medical status. Trial outcomes

9.1 Primary outcome measure

Time to complete healing (defined as intact skin without a scab) is recommended as an outcome to be included in research by the Cochrane Collaboration Wound Review Group and a 24 week follow up period is considered a minimum. Time to event data will be obtained from clinical records. District nurses visit patients on a weekly basis as part of normal care and record healing (average number of district nurse visits was 1.1 per week in the HALT trial). At 24 weeks, the Research Nurse will determine if the reference ulcer is healed. If the reference ulcer is healed, the research nurses will access clinical records to determine the date of healing was first reported during the 24-week period. If the reference ulcer is unhealed, the Research Nurse will determine from the clinical record whether the reference ulcer had healed at any time prior to 24 weeks. If there is no mention of healing then the ulcer will be assumed to have been unhealed during the 24 weeks. If the reference ulcer is recorded as healed during that time, the unhealed ulcer will be assumed to be a recurrent ulcer and the date healing is first recorded will be assumed to be the healing date.

9.2 Secondary outcome measures

The following secondary outcome measures will be assessed in all participants at 24 weeks after randomisation:

- Proportion of participants with a healed reference VLU at 24 weeks.

- Estimated change in ulcer area – obtained from measuring maximum width and length of reference ulcer at baseline and endpoint and the ulcer area at each time point estimated using the calculation for area of an ellipse.⁵⁰ See rationale above for not using more complex methods of ulcer measurement.
- Change in HRQoL: Measured at baseline and at 24 weeks. Each person's perception of his or her general health will be assessed using the RAND 36-item Health Survey (a version of SF-36), EQ5D and ulcer-related health using the CXVUQ.^{51,52} The EQ5D and SF-36 are well-validated questionnaires for assessing quality of life in New Zealand and generating utility values for economic analyses.^{53,54 55,56} However, they may not be as responsive as a disease-specific instrument to changes in ulcer state (healed *versus* unhealed) over the short-term.^{22,57} Consequently, the CXVUQ will also be used, as it has been found to be very responsive to changes in VLU healing state.²²
- Adverse events: Measured throughout the 24-week follow up. Standard definitions of adverse events will be used and adverse events reports will be reviewed by one of the medically-qualified co-investigators and coded using the ICD-10 AM. All participants will be issued with a Clinical Trial Card, stating their participation in the trial and the possibility they are receiving low dose aspirin. If the participant presents with signs and symptoms of a serious adverse event, such as myocardial infarction, stroke, or extra-cranial bleed, the Clinical Trial Card will recommend they discontinue trial treatment and appropriate treatment initiated. These participants will still be included in follow up at 24 weeks.
- Treatment adherence: Measured at 24 weeks by count of remaining capsules by the Research Nurse.
- Efficacy of blinding: Measured at 24 weeks, the efficacy of blinding will be tested by asking patients which treatment they believed they received, and asking the same question of the research nurses.

10. Data collection and follow-up

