Investigators and Trial Centres: The overall design and conduct of this investigator-initiated study will be the responsibility of the Steering Committee. This a collaborative trial designed and coordinated jointly by independent investigators at the National Institute of Health Innovation (University of Auckland), the Dept. of General Practice and Primary Care (University of Auckland), and Auckland District Health Board, with input from clinicians at Auckland DHB, Counties Manukau DHB, Waikato DHB, the Nurse Maude Association Christchurch, and the Southern DHB. Publication of data from this trial will be the responsibility of the Steering Committee. The trial will be co-ordinated from the NIHI, with participants recruited from patients attending the district nursing services at Auckland DHB, Counties Manukau DHB, Waikato DHB, the Nurse Maude Association Christchurch, and the Southern DHB.

Trial Period: Oct 2014 – Oct 2017

Clinical Phase: Phase III

Objectives: The objective of this trial is to determine the effectiveness of low dose aspirin compared to placebo when used in addition to compression therapy for venous leg ulcer healing.

Duration of Treatment: The maximum duration of treatment is 24 weeks (or less if the ulcer heals within 24 weeks).

Trial Design and Methodology

A prospective community-based, double-blind, placebo-controlled, randomised trial with participants receiving either 150 mg aspirin daily for up to 24 weeks or matching placebo. Block randomisation will be used, stratified by trial centre and prognostic index (ulcer size and duration) to ensure a balance of participants within trial centres and for participants likely to be slow healers. Participants in both arms will also receive compression therapy (with system of choice guided by patient and/or clinical preference) as delivered through district nursing services at the trial centres. Assessment of health-related quality of life will be carried out at baseline and at the end of the trial treatment period. The patient will continue to receive district nursing care as per normal protocol.

Inclusion/exclusion criteria: Patients with leg ulcers will be eligible for *inclusion* if they meet the following criteria:

- Aged 18 years or older
- Determined to have a venous leg ulcer (clinical indications of venous ulceration, ABI \geq 0.8, and other causative aetiologies ruled out)
- Able to tolerate compression therapy
- Able to provide written informed consent

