11.2.2 Treatment effect

All data analyses will be carried out on an intention-to-treat basis⁶³. Time-to-event data will be analysed using Kaplan Meier plots and log rank test, and Cox regression will be used to take into account known covariates and the varying times since randomisation. The assumption of proportionality will be checked using standard graphical techniques. Simple incidence rates, relative risks, absolute risks and numbers needed to treat, and 95% CIs will be obtained for all binary outcomes in the first instance, with subsequent multiple logistic regression analysis conducted if necessary to adjust for imbalance in covariates. Continuous outcomes will be analysed using multiple linear regression and adjusted for baseline value and other covariates if needed. Adverse events will be analysed using incidence rate ratios. A *kappa* will be calculated for the evaluation of the efficacy of blinding. Should aspirin prove effective in the primary analysis, heterogeneity of effects on time to healing will be analysed using subgroups specified *a priori* in the Statistical Analysis Plan.

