11.2.3 Tolerability of treatment

All randomised participants will be included in this analysis. Comparison of the frequency of treatment withdrawal because of suspected intolerance between the aspirin group and the placebo group will be tested using Chi-square statistics. The number of participants discontinuing treatment prematurely for any reason will be summarized by treatment group and by reasons for discontinuation. The incidence of all suspected adverse treatment reactions will be summarized by treatment group.

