13.2 Notification of adverse events

During the trial information about AEs will be sought at the 6 month trial follow-up visit by the research nurse. AEs reported from the district nursing service or other health practitioners should be reported on a CRF X as soon as possible after notification.

AE data will be aggregated and reported by the trial statistician at intervals specified by the Data Safety Monitoring Board (DSMB).

Serious adverse events

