13.2.2 Notification of serious adverse events

Timely and complete reporting of all SAEs is necessary to identify events that are treatment related or potentially treatment related, thereby allowing: (1) a greater understanding of the overall safety profile of the treatment; (2) appropriate modification of trial protocols; and (3) adherence to regulatory requirements.

SAEs are to be documented on a CRF X and reported to the project manager within one day (24 hours) of detection. Participant deaths or SAEs that occur within 30 days after stopping the trial treatment should also be reported.

All CRF Xs require sign off by the authorised medical practitioner at NIHI who will assess the AE (blinded to treatment allocation) to determine whether the AE is a possible SAE.

If the AE is a possible SAE, the participant will be withdrawn from treatment, the trial treatment collected by the research nurse and the possible SAE will be notified to the participant’s GP.

The Principal Investigator will have the overall responsibility of ensuring that all events are reported to the regulatory authorities in the appropriate timeframes. The project manager will have the responsibility to ensure that SAEs are appropriately monitored and reported. As participants with AEs will not be unblinded during the trial, there will be no expedited reporting on serious suspected adverse drug reactions.

Participants experiencing AEs that cause interruption or discontinuation of trial treatment, or those experiencing SAEs that are present at the end of their participation in the trial will receive follow-up as appropriate, which may involve referral to the participant’s general practitioner.

All AEs will be classified by a medical coder at the NIHI who will be blind to treatment allocation. Standard definitions of adverse events will be used and graded using the Common Terminology Criteria for Adverse Events v3.0.

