14.5 Treatment on completion of trial

Participants will be asked to return all unused aspirin capsules to the research nurse. Returned capsules will be disposed of at the end of the trial follow-up period by the Research Nurse in accord with local DHB protocol.

15. Relevance to Health

The trial contributes to the goal of improving outcomes for individuals and populations with disease as follows:

- *More people could be healed* - Even with good compression 30-60% of patients remain unhealed after 12 weeks of compression therapy in clinical trials.²⁴⁻²⁷ New Zealand trials suggest a baseline healing rate of 50% at 12 weeks and aspirin could increase this proportion to 65% at 12 weeks and 75% at 24 weeks.
- *Improved quality of life* - Ulcer healing improves quality of life,²² and earlier healing will increase patients' quality of life, especially in the older people who more commonly have leg ulcers.

The trial also contributes to the goal of cost-effective sustainable solutions as follows:

- *Reduced costs* - The average cost of 12 weeks venous ulcer treatment is NZ\$972, a figure inflated by patients that remain unhealed. The average cost of healed patients for a 12-week period is NZ\$535 compared to NZ\$1405 for those that remain unhealed.⁸ Increasing the number of patients healed early will decrease the overall spend on this patient group.
- *Reduced burden on district nursing services* - As people's ulcers heal they no longer need district nursing and other related services for leg ulcer management, freeing up these resources.
- *Easier access to a low cost, effective adjuvant* - Aspirin is a safe, inexpensive, over-the-counter medication, with very few barriers to patient use or practitioner recommendation.

16. Dissemination of Results

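### If capsules stop at healing, the 24-week intention-to-treat adverse event ratio understates on-drug harm, and the visit schedule collects no stop date from which to estimate it

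*Protocol*

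**What the plan says.** **Treatment period.** The synopsis (Duration of Treatment) says "The maximum duration of treatment is 24 weeks (or less if the ulcer heals within 24 weeks"). Section 4 gives only a maximum of 24 weeks. Section 9 does not list healing among the reasons for discontinuing. Section 14.2 dispenses 168 days of capsules at randomisation. The stop at healing is therefore explicit in the synopsis alone.

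**Safety window.** Section 9.2 has "Adverse events: Measured throughout the 24-week follow up". Section 9 keeps visits and data collection running after treatment is discontinued. For serious events, section 13.2.2 adds: "Participant deaths or SAEs that occur within 30 days after stopping the trial treatment should also be reported".

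**Analysis.** Section 11.2.2 says "All data analyses will be carried out on an intention-to-treat basis" and "Adverse events will be analysed using incidence rate ratios". For tolerability, section 11.2.3 says "All randomised participants will be included in this analysis". The protocol defines no on-treatment period.

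**Exposure data.** The schedule in section 10.2 and the Visit 3 list in section 10.6 include a count of remaining capsules at week 24. Neither lists the date of the last capsule.

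**The concern.** Read with the synopsis, treatment ends on the primary efficacy outcome while safety follow-up continues to week 24. Days after healing add background events to both arms but carry little or no drug effect, so a ratio over all 24 weeks is pulled towards 1. This happens whether or not aspirin speeds healing, and more so if it does.

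Adverse events are a stated aim (section 3). Section 2.7 justifies enrolling people older than 79 by the need for better evidence on risk and benefit at that age, and section 15 describes aspirin as safe. A reader asking about risk while taking aspirin would get an attenuated answer, and the scheduled data would not let the analyst recover a better one.

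**Working it through.** **Inputs.** Control median time to healing is 92 days and the difference sought is four weeks, so the aspirin median is 92 − 28 = 64 days (section 11.1). Follow-up is 24 × 7 = 168 days. The relative risk of upper gastrointestinal bleeding or perforation at 150 mg is 2.0, 95% CI 1.5 to 2.6 (section 2.7).

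**Assumptions.** Healing times are exponential, capsules stop at healing and for no other reason, the background event rate is constant, and no drug effect remains after stopping.

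**Check on the medians.** Schoenfeld's formula with 90% power and two-sided alpha 0.05 gives 4 × (1.960 + 1.282)² / [ln(92/64)]² = 42.03 / 0.1317 = 319.1, or 320 in two equal arms, against the stated 318. Then 318 / 0.9 = 353.3, rounded up to the stated 354. The formula counts healing events; it is used here only to confirm that 92 and 64 days are the planning medians.

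**Mean days on drug.** With h = ln 2 / median, the mean is (1 − exp(−168h)) / h. The ratio over all 24 weeks is 1 + (RR − 1) × (days on drug / 168).

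| Aspirin-arm median | Days on drug | Off drug | RR 2.0 reads as | RR 1.5 and 2.6 read as |
|---|---|---|---|---|
| 64 days (planned effect) | 77.4 | 53.9% | 1.46 | 1.23 and 1.74 |
| 92 days (no effect on healing) | 95.3 | 43.3% | 1.57 | 1.28 and 1.91 |

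**Absolute excess.** Let b be the background rate per day. With the 64-day median, the aspirin arm expects 2b × 77.4 + b × 90.6 = 245.4b events per participant and the placebo arm 168b. The ratio is 245.4 / 168 = 1.46 and the excess is 77.4b. On treated time alone the same participants have 154.8b events where 77.4b would be expected without the drug. The ratio is 2.0 and the excess is again 77.4b. Only the ratio changes.

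**Sensitivity.**
- Section 15 suggests 65% healed at 12 weeks and 75% at 24 weeks on aspirin. With a constant hazard within each 12-week half, this gives 77.0 days on drug (45.8%), and 2.0 reads as 1.46.
- If the drug effect lasts 7 to 10 days after stopping (an assumption), 2.0 reads as 1.50 to 1.51 (planned effect) or 1.60 to 1.61 (no effect on healing).
- If participants take capsules for all 168 days, there is no dilution. Stopping for other reasons would add to it.

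**Length of lag in an exposure-based analysis.** With a 30-day lag capped at week 24, the mean window is 30 + (1 − exp(−138h)) / h = 101.6 days (median 64) or 115.8 days (median 92). Then 2.0 reads as 1 + 77.4/101.6 = 1.76 or 1 + 95.3/115.8 = 1.82. A long lag brings part of the dilution back.

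**What a pill count can show.** Suppose a participant returns 84 of 168 daily capsules. That fits stopping at day 84, and equally fits taking one every second day to week 24. The count gives the amount taken, not the stop date.

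**The case against.** **Intention to treat is a legitimate safety estimand.** The trial tests treatment until healing in routine care, and the 24-week comparison measures the harm of that policy without selection after randomisation. This stands. A reader might infer that the comparison is wrong and should give way to an on-treatment one; the documents do not support that. On-treatment time is set by healing, over-represents slow healers, and does so differently by arm if aspirin works.

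**The denominator belongs in the SAP.** This stands in part. The SAP is not shown and may define at-risk time. The stop date, however, has to be collected at the visit, and the protocol's schedule does not list it. The forms are not shown either, so a field may exist. The healing date (section 9.1) is only a proxy, because no section says how a stop at healing is carried out or recorded.

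**Major bleeds will be too few.** This stands. Section 2.7 gives about 0.10% a year for extra-cranial bleeds on aspirin. With 177 participants, 177 × 168 / 365.25 = 81.4 person-years, so about 0.08 events are expected. The benefit lies mainly with commoner adverse events; the 2.0 illustrates dilution and does not forecast a result.

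**Stronger readings to avoid.**
- The 30-day rule might be read as limiting the SAE window, making it shorter in the faster-healing arm. Section 13.2.2 asks that such events also be reported, which adds to capture.
- Section 15 says that after healing "they no longer need district nursing and other related services for leg ulcer management", and section 13.2 that "information about AEs will be sought at the 6 month trial follow-up visit by the research nurse". A reader might infer that only recall at week 24 remains after healing. But section 13.2 also takes reports from other health practitioners, section 10.2 schedules adverse event capture over weeks 1 to 24, and participants carry a Clinical Trial Card (section 9.2).
- Nor do all these features push towards finding no harm. Dilution of the ratio does so regardless of efficacy; any difference between arms in exposure requires that aspirin change healing.

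**Conclusion.** The point holds as a limited, inexpensive improvement. If the synopsis rule is followed, 43% to 54% of the aspirin arm's follow-up is off drug, and an on-drug ratio of 2.0 reads as about 1.57 to 1.46 over 24 weeks. This rests on exponential healing at the planning medians, a constant background rate, no carry-over and no other discontinuation, and it shrinks to the extent that participants keep taking capsules after healing. The planned comparison is valid for the treat-until-healed policy and preserves the absolute excess, but it should not be read as conservative for harm on drug. What needs correcting is that the treatment period is described inconsistently and that no scheduled item dates the end of exposure.

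**What to change.** 1. Keep the all-randomised 24-week comparison as the main safety analysis.
2. Add the date of last capsule to Visit 3 (sections 10.2 and 10.6).
3. In section 11.2.2, pre-specify a supplementary rate ratio on treated person-time plus a stated short lag. Note there that this time is determined by healing and so is open to selection.
4. Reconcile the synopsis statement on stopping at healing with section 4, the discontinuation reasons in section 9 and the 168-day supply in section 14.2. Which rule applies is for the investigators.
5. State how the 30-day SAE reporting in section 13.2.2 relates to the 24-week window in section 9.2, including for participants whose 30 days run past week 24.

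The cost is one form field, one extra table and some wording. The supplementary table will have wider intervals, and some last-capsule dates will be recalled rather than recorded at the time.
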